#### 4.1.2 MMRM assuming a normal distribution

An MMRM will be fitted on percent change from baseline. Percent change from baseline is calculated as the visit value minus the baseline value divided by the baseline value \*100.

The visit statistically tested within the MMRM is week 12 (day 85). All previous available data on scheduled visits will be used in the model. Fixed factors of the model will be treatment, visit and treatment\*visit interaction. The baseline value of the outcome variable will be used as a covariate. Visits within subjects will be considered as repeated measurements.

Comparisons derived from the model will be:

- AZD8233 **CCI** versus placebo,
- AZD8233 **CCI** versus placebo
- AZD8233 **CCI** versus placebo
- AZD8233 **CCI** versus AZD8233 **CCI**
- AZD8233 **CCI** versus AZD8233 **CCI**
- AZD8233 **CCI** versus AZD8233 **CCI**

The REML approach will be used for the estimation of the variance and covariance parameters of the linear mixed model; two-sided difference test, with alpha level at 5% will be used for the comparisons and for the t-type confidence interval calculation.

The model will be fitted with an unstructured covariance structure and the Kenward-Roger correction applied to obtain the degrees of freedom.

In case the model will not converge for any reason, the following hierarchical model fitting procedure will be adopted:

1. The MMRM will be fitted using a SP(POW) covariance structure; Visit will be expressed as scheduled visit days to accomplish the variance-covariance matrix estimation.
2. The MMRM will be fitted using a CS covariance structure.
3. An ANCOVA model will be used.

The reportable results from the model will be:

- The LSmean and their 95% CI for each group for the percent change from baseline
- The LSmean of the difference between active groups and the control group
- The 95% CI of the LSmean of the difference
- P-value of the LSmean of the difference

#### **4.1.3 Sensitivity analysis 1**

The sensitivity analysis 1 will consist of repeating the MMRM assuming a log-normal distribution including only subjects who have completed the treatment period as per protocol and who have no relevant IPDs. Subjects who have completed the treatment period as per protocol are the subjects who reached week 12 and received all four scheduled doses of IP; subjects who received wrong dose of IP or wrong treatment will be excluded. Further, relevant IPDs are defined in section 2.2.

#### **4.1.4 Sensitivity analysis 2**

The sensitivity analysis 2 will consist of repeating MMRM assuming a log-normal distribution (without any back-up strategy) using the pattern-mixture model with control-based pattern imputation ([reference 1](#)). To implement this approach, we firstly use MCMC to impute non monotone MAR missing data for subjects who have completed the treatment period as per protocol (reached week 12 and received all four doses of IP). Then we use the resulting dataset to sequentially impute missing data at each visit using a monotone regression approach. Sequential imputation will be done in two ways:

- considering only placebo group for the estimations of missing data for placebo patients and for active subjects at visits for which the previous scheduled dose of IP is missing or not as per protocol (wrong dose of IP or a wrong treatment);
- considering only the relevant active group for the estimations of missing data for active subjects at visits for which the previous scheduled dose of IP was taken as scheduled.

The results from each imputation set will be combined using Rubin's formulas

## **4.2 Analysis of variables**

### **4.2.1 Disposition of subjects**

Subject dispositions (number and percentage of subjects enrolled, subjects randomized, subjects who received at least one dose of study IP, subjects who completed the treatment and subjects who completed the study) will be presented in a summary table for each treatment group and overall. A listing including all standardized disposition terms will also be provided for all discontinued subjects. Both, the table and the listing will be based on all enrolled subjects.

Subjects affected by the COVID-19 pandemic and Subjects with reported issues in the Clinical Trial Management System due to COVID-19 pandemic will also be listed.

The number of subjects belonging to each analysis population will be presented in a separate summary table for each treatment group. The table will be based on all enrolled subjects. Listings of all subjects excluded from the full analysis set and from the safety analysis set will also be provided. The listings will include reason for exclusion from respective population and will be based on all enrolled subjects.

Randomization code and actual kit are also listed.

### **4.2.2 Important protocol deviations**

The number and percentage of subjects with at least one IPD will be summarized following the NHP categories, for each treatment group and overall, for the full analysis set. All the IPDs as reported in the CTMS (pre-treatment and on treatment) will be included in the table. All IPDs will also be listed for all subjects included in the full analysis set.

### **4.2.3 Baseline assessment and other subject-specific characteristics**

#### **4.2.3.1 Demographic and subject-specific characteristics**

All demographic and subject-specific characteristics reported in section 3.2.1 will be presented in summary tables for each treatment group and overall; Age, height, weight and BMI will be summarized descriptively as continuous variable with n, mean, median, SD, minimum, and maximum; all the other demographic and subject-specific characteristics will be summarized as categorical variables with the number and percentages of subjects by categories. Only the baseline measurement for height, weight and BMI will be considered in these tables. Baseline and post-baseline definitions are detailed in section 3.1.2. All demographic and subject-specific characteristics will also be provided in listings. The tables and the listings will be based on the full analysis set.

Recruitment by region country and centre will also be summarized.

#### **4.2.3.2 Medical history**

Any relevant medical histories and prior procedures as described in section 3.2.2 will be presented in summary tables as number and percentages of subjects by SOC and PT for each treatment group and overall. Subjects with multiple medical histories in the same SOC/PT will

be counted only once in that SOC/PT. Subjects with medical histories in more than one SOC/PT will be counted once in each of those SOC/PT. Tables will be sorted alphabetically by SOC and PT. The table will be based on the full analysis set.

#### **4.2.3.3 Nicotine and alcohol use**

Nicotine and alcohol use as described in section 3.2.3 will be presented in summary table as number and percentages of subjects for each treatment group and overall for the full analysis set.

#### **4.2.4 Primary / Secondary efficacy endpoints**

##### **4.2.4.1 Change from baseline in log-transformed LDL-C and percent change from baseline in LDL-C**

dLDL-C is described in section 3.3.1.1 and in section 3.3.2.2. Baseline and post-baseline definitions are detailed in section 3.1.2. Tables and listings will be based on the full analysis set and presented for each treatment group.

dLDL-C will be summarized descriptively as a continuous log-normal variable at each analysis visit and for relative change and percent change from baseline. Observed values will also be presented in figure with geometric mean and 95% CI by visit. Percent changes from baseline will be presented in figure with mean and 95% CI by visit.

An MMRM assuming a log-normal distribution as described in section 4.1 on log-transformed change from baseline to week 12 will be presented.

Additionally, as secondary objective, an MMRM assuming a normal distribution as described in section 4.1 on percent change from baseline to week 12 will be presented.

Sensitivity analyses 1 and 2 as per section 4.1 will also be produced.

Finally, dLDL-C will also be reported in a listing.

The correlation of LDL-C Friedewald and LDL-C Martin-Hopkins towards dLDL-C will also be estimated. The correlations are estimated using the mixed model approach, considering the two measurements as random effect in the model, and visits within subject as repeated measurements. Data are log-transformed to fulfil normal distribution criteria. Bland-Altman scatter plot on log-transformed data will also be shown.

#### **4.2.5 Secondary efficacy endpoints**

##### **4.2.5.1 Change from baseline in log transformed PCSK9**

PCSK9 is described in section 3.3.2.1. Baseline and post-baseline definitions are detailed in section 3.1.2. Tables and listings will be based on the full analysis set and presented for each treatment group.

PCSK9 will be summarized descriptively as a continuous log-normal variable at each analysis visit and for relative change and percent change from baseline. Observed values will also be presented in figure with geometric mean and 95% CI by visit. Percent changes from baseline will be presented in figure with mean and 95% CI by visit.

An MMRM assuming a log-normal distribution as described in section 4.1 on log-transformed change from baseline to week 12 will be presented.

Finally, PCSK9 will also be reported in a listing.

#### **4.2.5.2 Level of other lipid parameters**

The other lipid parameters are listed and described in section 3.3.2.4. Baseline and post baseline definitions are detailed in section 3.1.2. Tables and listings will be based on the full analysis set and presented for each treatment group.

All lipid parameters will be summarized descriptively as continuous log-normal variables at each analysis visit and for relative change and percent change from baseline.

An MMRM assuming a normal distribution as described in section 4.1 on percent change from baseline to week 12 will also be presented.

Percent changes from baseline will be presented in figure with mean and 95% CI by visit.

All other lipid parameters will also be reported in a listing.

#### **4.2.5.3 Pharmacokinetic parameters**

The analysis will be based on the PK analysis set.

Plasma concentrations will be summarized descriptively as a continuous log-normal variable at each analysis visit and scheduled time. The geometric mean +/- the geometric standard deviation will be also reported together with the number of samples below the limit of quantification. The geometric mean +/- the geometric standard deviation is calculated as the  $\exp(\text{mean}(\text{variable in log}) \pm \text{SD}(\text{variable in log}))$ . Plasma concentrations will also be listed for all subjects in the PK analysis set. Listings of all subjects excluded from the PK analysis set will also be provided. The listing will be based on all enrolled subjects.

PK parameters are not derived and analysed within this SAP. Derivations and results of the pharmacokinetic analyses are provided in an additional bioanalytical report prepared by a dedicated pharmacometrics support group at AstraZeneca.

#### **4.2.5.4 Immunogenicity**

The analysis will be based on the ADA analysis set.

Immunogenicity parameters are described in section 3.3.2.5. Baseline and post-baseline definitions are detailed in section 3.1.2. Immunogenicity parameters tables and listings will be based on the ADA analysis set and presented for each treatment group.

ADA will be summarized as categorical variables with the number and percentages with a positive result at the specific visit. Immunogenicity titre will be summarized descriptively as a continuous variable, only for ADA positive tests, with median, interquartile range, minimum, and maximum, at each analysis visit.

ADA will also be summarized including the following:

- ADA positive at baseline and/or post-baseline (ADA prevalence)
- TE-ADA positive (ADA incidence)
- Treatment-induced ADA positive
- Treatment-boosted ADA positive
- TE-ADA negative
- Both baseline and post-baseline positive
- Only baseline positive
- ADA persistently positive
- ADA transiently positive
- TE-ADA positive with maximum titre > median of maximum titres

Post baseline coincide with the on-treatment phase as described in section 3.1.3.

Treatment-induced ADA positive is defined as ADA negative at baseline and post-baseline ADA positive

Treatment-boosted ADA positive is defined as ADA positive at baseline and boosted the pre-existing titre post-baseline ( $\geq 4$ -fold increase).

TE-ADA positive is defined as the sum of treatment-induced ADA positive and treatment-boosted ADA positive.

TE-ADA negative is defined as ADA positive but not fulfilling the definition of TE-ADA positive.

ADA persistently positive is defined as either ADA negative at baseline and ADA positive at  $\geq 2$  post-baseline assessments (with  $\geq 16$  weeks between first and last positive) either ADA positive at last post-baseline assessment.

ADA transiently positive is defined as ADA negative at baseline, having at least one post-baseline ADA positive assessment and not fulfilling the conditions of ADA persistently positive.

The median of maximum titres is calculated based on the maximum titre for each ADA positive subject within each treatment group (including both baseline and post-baseline measurements).

Missing ADA results are considered negative for the derivation of the above categories. The above categories will be calculated only for subjects in the ADA analysis set.

All immunogenicity parameters will also be reported in a listing for the full analysis set. Days from previous dose of IP will be calculated as the ADA date minus date of previous dose +1. Days from previous dose of IP for ADA measured during pre-treatment period will be set to missing. Listings of all subjects excluded from the ADA analysis set will also be provided. The listing will be based on all enrolled subjects.

The following figures will be also provided for complete analysis only:

A spaghetti plot figure with individual plotted ADA-titres over time in subjects with any positive ADA-response, one graph per treatment group (including placebo).

A boxplot exploring ADA positive vs ADA negatives impact on PK concentrations over time, percent change on PCSK9 and percent change on LDL over time, one graph per treatment group (including placebo).

A figure showing the percentage of subjects with positive ADA results over time.

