**Table 1 Schedule of Activities (SoA)**

|              | Screening                   |               | Treatment Period |             |                |             |                |             |                | EDV | Safety Follow-up period   | Final Follow-up Visit | Details in CSP Section or Appendix |
|--------------|-----------------------------|---------------|------------------|-------------|----------------|-------------|----------------|-------------|----------------|-----|---|-----------------------|------------------------------------|
| Visit Number | 1                           | 2             | 3                | 4           | 5 a | 6           | 7 a | 8           | 9 a |     | 10, 11 a ,
12, 13 a ,
14, 15 a | 16                    |                                    |
| Study Week   |                             |               | 0                | 1           | 3              | 4           | 6              | 8           | 10             |     | 12, 14,
16, 18,
20, 22  | 24                    |                                    |
| Study Day    | D-42 to
D-1 l | D-7 to
D-1 | D1               | D8          | D22            | D29         | D43            | D57         | D71            |     | D85,
D99,
D113,
D127,
D141,
D155                       | D169                  |                                    |
| Visit Window |                             |               |                  | ± 1
days | ± 2
days    | ± 2
days | ± 2
days    | ± 2
days | ± 2
days    |     | ± 2
days   | ± 2
days           |                                    |

i PK sampling to be performed at Visits 4 (D8), 6 (D29), 7 (D43), 8 (D57), 9 (D71), 10 (D85), 12 (D113) and 14 (D141) and final follow-up visit/EDV. Schedule of sampling for Visits 4 (D8), 6 (D29), 8 (D57) are shown below.

Visit 4 (Day 8; Loading dose): pre-dose

Visit 6 (Day 29; Dose 3): pre-dose

Visit 8 (Day 57; Final dose): pre-dose

j ADA sampling to be performed at Visits 3 (D1), 4 (D8), 6 (D29), 8 (D57), 10 (D85), 12 (D113), and 14 (D141), and final follow-up visit/EDV. ADA samples to be collected pre-dose on all dosing days.

k If, for any reason, the sample is not drawn pre-dose on Visit 3 (D1), it may be taken at any visit until the Final follow-up/EDV visit.

l Visit 1 and visit 2 may be combined.

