
 
To collect and store blood (plasma) and urine samples for potential future exploratory research aimed at exploring biomarkers involved in PK, PD, safety (including anti-platelet antibodies) and tolerability related to AZD8233 treatment or cardiometabolic diseases
 
	
 
Results of potential future exploratory biomarker research may be reported outside this study's CSR
 

 
Optional: To collect and store DNA from blood samples according to each country's local and ethical procedures for future exploratory research into genes/genetic variation that may influence response to treatment.
 
	
 
Results of possible future genetic research may be reported outside this study's CSR.
 

Two analyses are planned for this study:

- A primary analysis after the treatment period,
- A complete analysis after the final follow-up (after final database lock).

[figure not shown]
The two analyses will have the same scope, except for lipoprotein profile which will be included only in the complete analysis, as described in sections 2, 3 and 4. With the aim to maintain the blinding the primary analysis will be performed by an independent unblinded team. The purpose of the primary analysis is to help inform further clinical development; no changes will be made to this study unless a safety signal is observed. This analysis will not have any impact on the overall type-1 error because no changes will be made to the trial based on the outcome of the analysis (all efficacy data is already collected at the point of the primary analysis, no changes to the efficacy model will be made). The primary analysis will be done when all patients still in study have completed the treatment period (visit 10). Additional details will be given in the primary analysis charter and the Unblinded Review Committee (URC) charters (i.e. data cut-off rules, data cleaning, nomination of the unblinded biometrics team and the URC and the operational procedures used to protect the blinding).

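### As worded, the persistent-ADA category admits unboosted pre-existing ADA, and its 16-week route cannot be met on data that end at Visit 10

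*SAP*

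**What the plan says.** **Definitions (SAP 4.2.5.4).** The first route to persistence is worded "ADA persistently positive is defined as either ADA negative at baseline and ADA positive at" two or more post-baseline assessments, with at least 16 weeks from first to last positive. The second route is only "either ADA positive at last post-baseline assessment". For the transient category the SAP says: "ADA transiently positive is defined as ADA negative at baseline, having at least one post-baseline ADA positive assessment and not fulfilling the conditions of" the persistent category. Treatment-induced means negative at baseline and positive later. Treatment-boosted needs at least a four-fold rise over a pre-existing titre. TE-ADA positive is those two groups together, and TE-ADA negative is any other ADA-positive participant. Missing results count as negative. The post-baseline period is the on-treatment phase, which SAP 3.1.3 (Table 5) runs to the end of study.

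**Scope and timing.** SAP 1.1 says of the primary and complete analyses: "The two analyses will have the same scope, except for lipoprotein profile which will be included only in the complete analysis". SAP section 4 applies its methods to both, and SAP 8.1.2 records that ADA tables were added at the primary analysis. Within 4.2.5.4 only the ADA figures are held back. The trigger is completion of Visit 10 by everyone still in the study; SAP 1.1 leaves the data cut-off rules to charters.

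**Sampling (Protocol Table 1, footnote j).** ADA samples are due on Days 1, 8, 29, 57, 85, 113 and 141 and at the final follow-up (Day 169) or early discontinuation visit, pre-dose on dosing days. The first scheduled post-baseline sample is therefore Day 8.

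**The concern.** There are two separate problems.

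1. The persistent category can take in people whose ADA was there before treatment and did not change. The transient category cannot, because it requires a negative baseline. The two rows sit side by side in one table and look like a split of treatment-induced ADA, which on the literal wording they need not be. This affects both analyses.
2. A 16-week criterion is to be tabulated at an analysis triggered at Week 12. Immunogenicity is a secondary objective, and SAP 1.1 says the primary analysis is meant to inform further development. A reader of that table could take the persistent row to mean sustained ADA when, for some or all participants, it means only a positive latest sample.

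**Working it through.** **Part 1: the definition.** Take a participant who is ADA positive at baseline, has no four-fold rise, and is positive at the last sample.

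| Category | Met as worded? | Why |
|---|---|---|
| Persistent, route 1 | No | Baseline is positive |
| Persistent, route 2 | Yes | Last sample is positive; nothing else is asked |
| Transient | No | Baseline is positive |
| Treatment-induced | No | Baseline is positive |
| Treatment-boosted | No | Rise is below four-fold |
| TE-ADA negative | Yes | ADA positive but neither induced nor boosted |

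Listing every positive/negative sequence for a baseline-positive participant:

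- Four samples to Day 85: 2^4 = 16 sequences. Persistent as worded: 8. With a negative baseline required in both routes: 0.
- Seven samples to Day 169: 2^7 = 128 sequences. Persistent as worded: 64. With the condition in both routes: 0.

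Baseline-negative participants are classified identically under either reading.

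**Part 2: the 16-week route.** The plan's own schedule reproduces: Day 85 is (85 − 1)/7 = 12.0 weeks, and Day 169 is (169 − 57)/7 = 16.0 weeks after the last dose. The criterion is 16 × 7 = 112 days.

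Longest gap between post-baseline ADA samples with data to Visit 10:

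| Basis | Calculation | Days | Weeks |
|---|---|---|---|
| Scheduled days | 85 − 8 | 77 | 11.0 |
| Protocol visit windows | 87 − 7 | 80 | 11.4 |
| SAP analysis windows (Table 3) | 87 − 6 | 81 | 11.6 |
| Day 1 sample of unknown time, treated as post-dose | 87 − 1 | 86 | 12.3 |

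All fall short of 112. Of the 16 sequences in a baseline-negative participant, none meets route 1. Eight are persistent, exactly those with a positive Day 85, and seven are transient; one has no positive. A first positive at Day 85 is persistent, while positives at Days 8, 29 and 57 followed by a negative at Day 85 are transient.

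Pairs that meet route 1 on scheduled days:

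- Day 8 to Day 141 (133 days) or Day 169 (161)
- Day 29 to Day 141 (112) or Day 169 (140)
- Day 57 to Day 169 (112)

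The later positive must therefore be a follow-up sample. The two pairs at exactly 112 days range from 108 to 116 within protocol windows, so visit timing alone can decide them. Day 8 to Day 113 is 105 days, at most 108 within protocol windows; it could qualify only at the extremes of the analysis windows (120 − 6 = 114).

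**Visit 10 cut against full follow-up.** Over the 128 full sequences in a baseline-negative participant, 20 move from persistent to transient and 40 from transient to persistent, so 60 change label. These count sequences; they are not probabilities.

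**Calendar cut (assumption).** A participant randomized about 141 − 85 = 56 days before the last one (52 to 60 with windows) would have reached Day 141 and could meet route 1. The documents give no accrual duration, so the share of such participants is unknown.

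**The case against.** **The repeated *either* is a language slip, and the negative baseline was meant for both routes.** This is plausible, and the transient definition fits it. But the word order does not say it, and a programmer following the text would code the wider rule. Protocol 8.5.2 supports the narrower intent: its persistence follow-up is for treatment-emergent ADA, not unchanged pre-existing reactivity.

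**The primary-analysis labels are not shown to rest on the last sample.** A reader might infer that they do so for everyone. The documents do not support that: Visit 10 of the last remaining participant is a trigger, the cut-off rule is in charters not supplied, and the post-baseline period runs to the end of study. The statement holds only for participants whose data end at Visit 10.

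**The effect is not quantified.** A reader might also infer that pre-existing ADA inflates the persistent row in every arm, placebo included, or that the two rows use different denominators. Neither is established. No pre-existing rate is given, and all categories are calculated in the one ADA analysis set; what differs is who can enter each count. Every baseline-negative participant with a later positive still falls into exactly one of the two rows.

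**The rows are descriptive and will be re-derived.** This stands. No test depends on them, pre-existing ADA is visible in other rows and the listing, and the complete analysis uses full follow-up. That limits the consequence but does not justify leaving the rule as worded.

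**Conclusion.** The point holds in two parts.

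- **Definition.** On the literal wording, the second route classifies unboosted pre-existing ADA with a positive last sample as persistent, overlapping TE-ADA negative. Persistent plus transient then need not equal treatment-induced ADA. The number of participants affected depends on a pre-existing rate that the documents do not give; it could be zero.
- **Timing.** With data ending at Visit 10, the 16-week route is out of reach (77 to 81 days against 112; 86 in the Day 1 edge case), and the label is set by the last sample. Under a calendar cut, the row would mix participants who could meet the route with participants who could not. Which applies depends on the unseen charter, but neither gives the row one consistent 16-week meaning.

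Because missing results count as negative, a missing last sample may also turn a positive participant transient. No efficacy analysis is affected.

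**What to change.** In SAP 4.2.5.4:

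- **(a)** Make a negative baseline a condition of the whole persistent category, then allow either route: two or more later positives spanning at least 16 weeks, or a positive final post-baseline sample. Persistent and transient then add up to treatment-induced ADA.
- **(b)** Report the persistent and transient rows only at the complete analysis, as is already done for the ADA figures. Alternatively, state the data cut in the SAP and label the two rows provisional at the primary analysis.

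The cost is a sentence or two of text and, under the first option in (b), two rows dropped from the primary-analysis table. Final persistence results wait for the final lock. Under (a), treatment-boosted participants also leave the persistent row, but they keep their own row in the same table.
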